- d) Once determined to be eligible, the paramedics will open the cooler, remove the two cassettes from the sealed bag, and open both cassettes to determine their contents. Once the cassettes are opened, the patient will be randomized to one of the 2 arms. If the cooler contains two units of AB-FP24, the patient is randomized to the experimental group. If the cooler contains non-infusable frozen water, the patient is randomized to the control group. All ambulances will be equipped with a Plasmatherm and a cooler storage box containing either plasma or noninfusable

frozen water. Before transfusing any fluids (likely immediately before drawing blood so as not to hinder patient care), paramedics will apply the noninvasive device for recording continuous waveform data. This device will remain on the patient for 24 hours and will begin obtaining critical physiological information as soon as the monitoring begins. Since this is an observational component of the study, there will be no changes made to the patient's care during this portion. Waveform data will not be used in the provision of subsequent care.

- e) If the patient is randomized to the control arm, the patient will be given intravenous normal saline as the initial resuscitation fluid with 2 large bore IVs based on the current ATLS guidelines. Subsequent care will proceed per institutional, ATLS guided resuscitation with acute pRBC administration determined by hemodynamic response and additional blood component administration guided by rTEG and coagulation panel assessment in conjunction with clinical scenario. The Massive Transfusion Protocol may be initiated using the ABC score⁶⁹ and heuristic evaluation of uncontrolled hemorrhage of the attending surgeon (See Appendix 1 for DHMC Massive Transfusion Protocol)

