- **3. Intent to treat analysis:** primary and secondary outcome data will be collected in all patients regardless of treatment received.⁸⁴ An "intent-to-treat" approach will be used for all primary/secondary outcome analyses, i.e., we will compare the outcomes of the two groups according to the group assignment at time of randomization, regardless of what treatment participants actually received. Phase 2 trial, this approach will allow a preliminary evaluation of the

effectiveness of the proposed treatment (in addition to the efficacy assessment), since the health care of the subjects reflects the health care available to civilian trauma. More details are given in the sections describing statistical analysis as well as the missing data prevention and treatment.⁸⁴

In addition to the "intent to treat" approach, this study design also supports that exploratory analyses assess the association between the dose of plasma received in the field and the primary/secondary outcomes, an equivalent to the estimand "Outcome Improvement in Tolerators" described by the Panel on Handling Missing Data in Clinical Trials.⁸⁴ This will provide information on possible "dose-response" patterns for Phase 3 trials.

- 4. Power analysis: Power analyses for each primary endpoint in Stage I and II were performed using Pass 11 (Hintze, J. (2011). PASS 11. NCSS, LLC. Kaysville, Utah, USA. www.ncss.com). All power analyses account for two interim analyses for a total of three sequential, equally spaced analyses, assuming attrition rates of 0%, 10%, and 20%.
- 5. Interim analyses: We planned 5 analyses (4 interim, 1 final), equally spaced, using the O'Brien-Fleming method to calculate two-sided boundaries, assuming a 95% confidence and 80% power. Spacing will be defined by number of enrolled patients. The first look at the data will be done when one third of the predicted total enrollment has been reached and all patients accrued have been observed for the total 28-day period or till death, whatever occurs earlier. The first interim analysis will be conducted when n=50, the second at n=100, the third at n=150, the fourth at n=200 and the final at end of the 5-year period of accrual.

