- 7. Waveform Data: We would like to collect more CRI data from very sick individuals to see how the algorithm captures their clinical presentation and resuscitation. We also want to see if a certain minimal CRI or low CRI for a period time triggers the acute coagulopathy of trauma. Just as other vital signs can be used to indicate certain medical conditions, we would analyze the data to see if the acute coagulopathy of trauma correlates with either a minimal CRI or low CRI for a certain period of time. We will also collate the CRI data with the clinical timeline of interventions, medications and fluids given. This will help us correlate the effects of the interventions, medications and fluids with changes in CRI.
 - a. Data analytics will be used to analyze the waveform data in relation to fluid resuscitation types, rates and volumes, response to fluid therapy, types of injuries, operative timing and management, length of ICU and hospital stay, as well as overall outcomes. We will compare the waveform features from trauma patients to those features collected from research subjects with analogous levels of LBNP applied.

E. Primary Study Objectives and Endpoints

 Primary Study Objective: to determine the efficacy, as measured by 28-day mortality reduction, of using postinjury field-resuscitation with plasma first compared to standard of care (SOC).

Primary Endpoint: 28-day mortality

a. **Definition:** 28-day mortality is defined as death within 28 days post injury (death of any cause except for death due to a second, clearly unrelated traumatic injury suffered after discharge). Research coordinators will verify the vital status of all patients at day 28. Patients

discharged home before day 28 will be reached using contact information obtained at discharge. In case of transfer or discharge to another facility before day 28, research coordinators will coordinate with the other facility to ascertain vital status, verify contact information at discharge or determine patient disposition at day 28 postinjury

- b. **Hypothesis**: 28-day mortality will be significantly higher^{*} in control patients compared to experimental patients.

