the patient to the hospital as soon as possible. Paramedics cannot assess competency of family members in this time-sensitive setting; thus family members that are not in shock or severely injured will be assumed to be competent.

- **8.** It will be assumed that patients will not be competent to give an assent since by nature of the eligibility criteria, the patient will be in severe shock.
- 9. If the patient will not be transported to Denver Health, he/she will not be enrolled. If the patient is enrolled, but due to unforeseen circumstances (such as impending airway), must be transported to a nearby facility that is not Denver Health, then the patient will be unenrolled. If possible, every effort will be made to contact the family and follow the patient for any adverse effects. The consent form will be used to verify that the patient (or family) was informed.

K. Procedures involving plasma

- 1. Procedure for thawing frozen AB-FP24: AB-FP24 will be thawed in the Plasmatherm (see section IV.L.2) and in accordance to the instructions accompanying the product and as approved by the FDA.
- **Plasma is thawed but not transfused:** If the AB-FP24 is thawed but not transfused for unforeseen reasons, such as discovery of Jehovah's Witnesses, then the unit(s) will be discarded or used for research purposes. It will not be transfused into humans.
- 2. Procedure for Issuing 2 units of AB-FP24: Bonfils Blood Center will be providing the AB plasma for the study.. This is modified from the DHMC policy for Blood Transfusions to be applicable to this study.
 - a. AB-FP24 will be administered through the standard Y-set with blood transfusion filter (170-260 micron).
 - b. Vital signs are required before the transfusion of all components and again after 15 minutes and at the completion of the transfusion. Transfusion rate will be compatible with the patient's condition. The patient will be monitored closely during the entire transfusion. The documented start and stop times are directly related to the actual transfusion of the component. Paramedics will document vital signs and start times in the field. Study coordinators will assume responsibility of additional vital signs and stopping time of the AB-FP24.
 - c. The patient medical record shall include the following:
 - **1.** Name of the components transfused
 - 2. Donor identification number of components
 - 3. Date and time of transfusion (Start and Stop time)
 - **4.** Pre and post transfusion vital signs

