 - b. Once the patient arrives at the hospital, the admissions department and social workers in the ED attempt to locate family members of the patient using every resource available, including several databases, previous medical records, and cellular phones. Within the trauma population, few of the patients have advance medical directives identifying a legally authorized representative (LAR). If no LAR was previously identified and there are several interested parties, per Colorado law, the social worker meets with all interested parties to select a proxy decision maker (See Appendix 5: Proxy Decision Maker). Continued diligent attempts by social workers to contact a legally authorized representative or family member of the patient will continue if the patient remains incapacitated.
 - c. Prisoners: If the patient becomes a prisoner during the study, they will be treated similar to non-prisoner subjects in accordance with DH policy of hospital care of patient-inmates. (see appendix 13)

d. Procedure for consent

- Once a LAR/PDM is available, a member of the study team will inform him/her of the study and obtain consent for continued collection of blood samples up to day 7 and clinical data up to day 28.
- If a LAR/PDM does not consent for continued data collection, no further blood draws and/or data collection will occur. The LAR/PDM will be asked if he/she would like the patient withdrawn from the study.
- 3. If a patient becomes competent to consent, a member of the study team will inform and re-obtain consent from the patient for continued data collection.
- 4. If a family member has consented for continued data collection, but when competent, the patient does not consent for continued data collection, no further blood draws and/or data collection will occur. The patient will be asked if he/she would like to be withdrawn from the study.
- 5. The LAR/PDM or the patient may withdraw from the study at any time, including at the time of consent. If the patient is withdrawn from the study, previously collected blood samples and data will be destroyed.
- 6. If a patient never regains decisional capacity and no LAR/proxy can be found, data and samples may be used since the subject has been enrolled under Exception for consent for emergency research. In this situation, all attempts at consenting will be documented.

e. Procedure to inform family of patients who died before consent is obtained

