- 1. After patient death, if applicable, social work and decedent affairs/coroner will be contacted for information about the social situation and family contact information.
- 2. In 2-4 days after patient death, call next of kin or family contact. If family members are met in person at any time after death and the timing is appropriate, inform the family in person.
- 3. During the call, verify address and mail information letter as follow-up or give the letter to family if met in person.
- 4. If no one answers the call, leave a message, if possible. If no response in 24 hours, call back. Repeat up to 3 times.
- 5. The rationale of this procedure is that 21 CFR 50.24 requires that information about the clinical investigation be provided to the LAR or family member of patients who died before consent is obtained, if feasible. In certain clinical situations, the family may not be local and may not come to the hospital, thus, we will call

the family members after a brief period of grieving. However, given the sensitive situation, we prefer in-person communication, and will engage family if appropriate. We will follow up with the information letter, either by mail or in person as appropriate, allowing family members to read it at a later date. If we are unable to contact family after 3 tries, we will consider informing the family as not feasible.

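### The rules that unenrol diverted patients and destroy withdrawn patients' data contradict the by-assignment mortality analysis and should be reconciled with it before the final look

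*Combined protocol and SAP*

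**What the plan says.** **The analysis commitment.** Section IV.B.1.d fixes the moment of randomisation: "Once the cassettes are opened, the patient will be randomized to one of the 2 arms". The arm is known from then on. Section IV.D.3 compares outcomes "according to the group assignment at time of randomization, regardless of what treatment participants actually received". Section IV.H commits to collecting the primary endpoint, including day-28 vital status, on everyone randomised in the field, including patients later excluded for any reason.

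**Rules that act after randomisation.**
- Diversion (IV.J, item 9): an enrolled patient who for unforeseen reasons "must be transported to a nearby facility that is not Denver Health, then the patient will be unenrolled". The only follow-up named is this: "If possible, every effort will be made to contact the family and follow the patient for any adverse effects".
- Withdrawal (IV.M.1.d, item 5): "If the patient is withdrawn from the study, previously collected blood samples and data will be destroyed".
- Refusal of further collection (IV.M.1.d, item 2): "If a LAR/PDM does not consent for continued data collection, no further blood draws and/or data collection will occur". Whether to withdraw is then asked separately.
- Death before consent (IV.M.1.e): the regulation cited requires that "information about the clinical investigation be provided to the LAR or family member of patients who died before consent is obtained". Nothing is asked of the family about the data.

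**Handling of unknown vital status (IV.H).** Patients whose status cannot be verified count as alive. If more than 5% are missing, two scenarios are run: every unknown died, or every unknown survived.

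**Loss so far.** The Addendum of November 16, 2016 (IV.E) reports that 88 of 100 enrolled patients could be analysed. It carries the 12% into the enlarged sample of 112 per group.

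**The concern.** The analysis sections include everyone randomised, while two operational sections take some of those patients, or their data, out again. Coordinators who follow IV.J and IV.M to the letter will not hold what IV.D.3 and IV.H require.

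Withdrawal also need not be independent of outcome. It can happen only when a representative or a competent patient has been approached. A patient who dies before anyone is asked stays in. So does one who never regains capacity and has no representative (IV.M.1.d, item 6). Diversion can likewise reflect the patient's condition, since the protocol's own example is an airway problem.

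The stake is the final mortality conclusion. At the Addendum's target effect, about 2 deaths are expected in the plasma arm (2% of 112), so a few misplaced patients could matter.

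**Working it through.** **Inputs.** From the Addendum: 112 per group, 12% v 2% mortality, final boundary 2.03100 (nominal alpha 0.042), 12% attrition. From IV.E: the two-sided Fisher exact test. From IV.H: under 2% predicted missing, and the 5% trigger. Differences are control minus plasma.

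**Plan's figures first.** (100 − 88)/100 = 12%, as stated. The boundary 2.03100 gives two-sided alpha 0.0423, as stated. Expected deaths are 0.12 × 112 = 13.4 and 0.02 × 112 = 2.2, so the nearest counts are 13 v 2.

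**1. Removed patients put back.** The base is 112 retained per arm. Each restored death adds one to that arm's deaths and denominator. These are assumed cases, not observations.

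| Restored deaths | Control | Plasma | p | Below 0.042? |
|---|---|---|---|---|
| none | 13/112 | 2/112 | 0.006 | yes |
| 2 plasma | 13/112 | 4/114 | 0.024 | yes |
| 3 plasma | 13/112 | 5/115 | 0.051 | no |
| 3 plasma, 1 control | 14/113 | 5/115 | 0.032 | yes |
| 3 plasma, 2 control | 15/114 | 5/115 | 0.020 | yes |

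The tipping count depends on the base. From 14/112 v 2/112, four plasma deaths are needed (6/116, p=0.062; three give 0.032). From 13/112 v 3/112, two are enough (5/114, p=0.052).

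**2. Balanced withdrawal of survivors.** If a share w of each arm withdraws and all are survivors, each observed rate is the true rate divided by (1 − w). At w = 5%: 12.6% − 2.1% = 10.5 points. At w = 12%: 13.6% − 2.3% = 11.4 points. The true difference is 10.0, so the shift is small.

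**3. The planned scenarios.** The trigger is 5% of 224 = 11.2, so 12 unknown starts the sensitivity analysis and 11 does not. Take 6 unknown per arm.

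| Scenario | Control | Plasma | Difference (points) | p |
|---|---|---|---|---|
| All unknown alive (also the main rule) | 13/112 | 2/112 | +9.8 | 0.006 |
| All unknown dead | 19/112 | 8/112 | +9.8 | 0.039 |
| Plasma unknown dead, control alive | 13/112 | 8/112 | +4.5 | 0.36 |
| Control unknown dead, plasma alive | 19/112 | 2/112 | +15.2 | 0.0001 |

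The first scenario adds nothing to the main analysis. With equal losses the second leaves the risk difference unchanged.

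Two cases limit this point. With 13 unknown per arm, the all-dead scenario does show the loss of significance (26/112 v 15/112, p=0.083). At the predicted level of under 2% (at most 4 of 224), with 2 unknown per arm, even the unfavourable arm-opposed extreme stays just significant (13 v 4, p=0.041).

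**The case against.** The other side has a good deal.

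- **The set is defined.** A reader might infer that the primary mortality set is undefined. It is not: IV.D.3 and IV.H together define it, and IV.J and IV.M then contradict it. Nor does IV.J say that an unenrolled patient leaves the analysis; it leaves the denominator unstated.
- **Refusal is different from withdrawal.** Declining further collection does not destroy data. It leaves a randomised patient with possibly unknown status, which IV.H already handles, and is not in itself a breach of intent-to-treat.
- **There are mitigations.** IV.H asks withdrawing patients for permission to verify mortality, and names the Trauma Registry and the Trauma Activation database as further sources of endpoint data. For transfers before day 28, IV.E says that "research coordinators will coordinate with the other facility to ascertain vital status". Transfused components are entered in the medical record (IV.K.2.c) and coolers are logged (Table 5), so the arm may be recoverable. All this stands as partial mitigation. None of it mentions unenrolled patients, the documents do not say that the registries reach patients taken elsewhere, and the destruction rule has no carve-out.
- **The 12 of 100.** A reader might infer that these show a breach, or that their vital status is unknown. Neither is supported. The reasons are in an interim report that is not among the documents, and some may rest on facts that predate randomisation, such as misjudged age (IV.N.4).
- **Three deaths.** A reader might infer that three removed plasma deaths would generally overturn the result. That needs three plasma deaths and no control death removed. The rules apply to both arms, and no passage suggests removal by arm.

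**Conclusion.** The conflict is explicit in the current text and should be fixed. Followed literally, the diversion and withdrawal rules turn the stated intent-to-treat comparison into one of retained patients, by a route that can depend on outcome. That conclusion rests on the wording alone and is firm.

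The size of any bias is not established. Loss of significance was found only with one-sided removal (p=0.051 with three plasma deaths restored), and a single restored control death reverses it (p=0.032). Balanced withdrawal of survivors moves a 10-point difference to at most 11.4 points across the 5% to 12% range. All counts are assumptions built on the Addendum's rates.

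The sensitivity scenarios are a secondary point. As planned, they can leave a result looking robust (p=0.039) when an arm-opposed extreme would not (p=0.36). This matters little if missing status stays below the predicted 2%.

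**What to change.** 1. Reconcile IV.J item 9 and IV.M.1.d with IV.D.3 and IV.H. State that every patient whose cassettes were opened stays in the primary denominator, by cooler content. Allow exclusions only on facts that predate randomisation, judged blind to arm.
2. Keep arm and day-28 vital status for diverted patients through the contact with other facilities in IV.E. For withdrawn patients, do so where permission allows, through the request already in IV.H.
3. State that the unknown-status rule in IV.H covers every randomised patient, including the unenrolled and withdrawn, and report these patients by arm.
4. Replace the scenario that counts all unknowns as survivors with arm-opposed extremes or a tipping-point table.

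**Cost.** Wording changes, plus modest vital-status retrieval: up to about 27 patients if 12% of 224 (26.9) had to be traced. The sensitivity range will be wider. Some withdrawn patients may stay unknown, and data already destroyed may not be recoverable.

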- a. Plasmatherm functions similarly to the typical water bath, however, the water does not contact the plasma, reducing the potential for contamination in the event of back breakage. If a bag breaks, Plasmatherm is easier to clean up than a typical water bath.

- b. Monthly, the Plasmatherm will be inspected for damage and cleaned. If there is any concern regarding the use of the Plasmatherm, the Pl will be notified. Before each shift, the display will be tested
- **3.** CipherOx M1 by Flashback Technologies is a non-FDA approved device consisting of an FDA-approved Nonin OEM III pulse-oximeter integrated with an ARM III processors, memory, a mini-USB port for charging and data off-load, as well as a high-resolution screen for indoor and outdoor use. The device collects non-invasive waveform data from acutely injured, potentially bleeding trauma patients. The device displays the date/time and an image of a finger with a sensor that is displayed in "green" if the data collection is "good." The providers are blinded to all physiological data collection by the device.

M. Special Consent Issues

- 1. We have requested an exception from informed consent for emergency research under 21 CFR §50.24 as the patients selected for enrollment in this clinical study will be unable to provide prospective informed consent due to the extent of their injuries and their immediate need for resuscitation from life-threatening hemorrhagic shock. These patients are often unable to give consent upon arrival, and this study cannot be carried out without an exception from informed consent.
 - a. The therapeutic window dedicated to obtaining prospective informed consent from the patient or a legally authorized representative is very brief. On average, line-placement has been accomplished by experienced field care personnel in approximately one minute, and therefore, the process of patient assessment, scene care, randomization, enrollment, thawing of plasma, and the start of AB plasma infusion can be expected to occur in less than 8 min. The opportunity to obtain prospective informed consent from the patient or a legally authorized representative or to provide an opportunity for a family member to object to the subject's imminent enrollment in the study may not be possible prior to the commencement of study procedures.
 - b. Once the patient arrives at the hospital, the admissions department and social workers in the ED attempt to locate family members of the patient using every resource available, including several databases, previous medical records, and cellular phones. Within the trauma population, few of the patients have advance medical directives identifying a legally authorized representative (LAR). If no LAR was previously identified and there are several interested parties, per Colorado law, the social worker meets with all interested parties to select a proxy decision maker (See Appendix 5: Proxy Decision Maker). Continued diligent attempts by social workers to contact a legally authorized representative or family member of the patient will continue if the patient remains incapacitated.
 - c. Prisoners: If the patient becomes a prisoner during the study, they will be treated similar to non-prisoner subjects in accordance with DH policy of hospital care of patient-inmates. (see appendix 13)

d. Procedure for consent

- Once a LAR/PDM is available, a member of the study team will inform him/her of the study and obtain consent for continued collection of blood samples up to day 7 and clinical data up to day 28.
- If a LAR/PDM does not consent for continued data collection, no further blood draws and/or data collection will occur. The LAR/PDM will be asked if he/she would like the patient withdrawn from the study.
- 3. If a patient becomes competent to consent, a member of the study team will inform and re-obtain consent from the patient for continued data collection.
- 4. If a family member has consented for continued data collection, but when competent, the patient does not consent for continued data collection, no further blood draws and/or data collection will occur. The patient will be asked if he/she would like to be withdrawn from the study.
- 5. The LAR/PDM or the patient may withdraw from the study at any time, including at the time of consent. If the patient is withdrawn from the study, previously collected blood samples and data will be destroyed.
- 6. If a patient never regains decisional capacity and no LAR/proxy can be found, data and samples may be used since the subject has been enrolled under Exception for consent for emergency research. In this situation, all attempts at consenting will be documented.

e. Procedure to inform family of patients who died before consent is obtained

- 1. After patient death, if applicable, social work and decedent affairs/coroner will be contacted for information about the social situation and family contact information.
- 2. In 2-4 days after patient death, call next of kin or family contact. If family members are met in person at any time after death and the timing is appropriate, inform the family in person.
- 3. During the call, verify address and mail information letter as follow-up or give the letter to family if met in person.
- 4. If no one answers the call, leave a message, if possible. If no response in 24 hours, call back. Repeat up to 3 times.
- 5. The rationale of this procedure is that 21 CFR 50.24 requires that information about the clinical investigation be provided to the LAR or family member of patients who died before consent is obtained, if feasible. In certain clinical situations, the family may not be local and may not come to the hospital, thus, we will call

the family members after a brief period of grieving. However, given the sensitive situation, we prefer in-person communication, and will engage family if appropriate. We will follow up with the information letter, either by mail or in person as appropriate, allowing family members to read it at a later date. If we are unable to contact family after 3 tries, we will consider informing the family as not feasible.

- 2. Community Consultation and Public Disclosure (CCPD): Protection of the rights and welfare of patients is necessary in all clinical studies and is paramount in studies involving vulnerable populations. Because this study involves victims of trauma who likely will not be able to provide informed consent or actively refuse enrollment, patients are placed in particularly vulnerable circumstances. This lack of autonomy creates a special need for FDA, sponsors, IRBs, and clinical investigators to work closely together to ensure that the interests of this vulnerable patient population are protected to the maximum extent possible. For such studies to be conducted, investigators must provide an opportunity for dialogue with the community in which a study will be conducted and from where subjects will be drawn. The IRB, Department of Defense, and the investigators will coordinate these efforts using the plan outlined in Appendix 6 Community Consultation and Public Disclosure Plan and Appendix 7 List of Neighborhoods and HOAs around Denver Metro Area. Discussion with the information disseminated to the community will adhere to 21 CFR §50.24 and 56.115.
 - a. In brief, the community consultation and public disclosure plan required by the 21 CFR §50.24 will include feedback from community meetings, online and social media feedback as well as paid advertisements, media news releases to TV, radio and newspapers, and women's health and community clinics. In addition, prior to initiation of the study, the clinical investigators and IRB will make arrangements for public disclosure of the plans for the investigation and a balanced disclosure of the risks and potential benefits to patients enrolled in the study. This disclosure will also include background information about the study, a synopsis of the protocol and study design, risks and benefits of fresh frozen plasma versus the standard crystalloid fluid, the selection of subjects, the use of provisions for exception from informed consent requirements and the process for attempting to contact a legally authorized representative, and the ways in which subjects can communicate their desire not to participate. Following the completion of the study, a summary of the findings of the clinical trial will be disseminated to the community. This information, presented to the community, is in language that is understandable and does not promote fresh frozen plasma, and will include the results of the trial and demographics of the patients enrolled.
 - Under 21 CFR §50.24, we submitted an Investigational New Drug Application (IND# 15216) for the use of thawed plasma in the resuscitation of severely injured trauma patients in an emergency

research protocol, which is necessary to obtain a waiver of consent in emergency research.

3. Under Title 10 US Code Section 980, Department of Defense funds may not be used for human research unless an informed consent of the subject or a legally authorized representative of the subject is obtained in advance for human subjects research. The Secretary of Defense may waive this prohibition for a specific research project to advance the development of a medical product necessary to the armed forces if the research project may directly benefit the subject and is carried out in accordance with all other applicable laws.

The contract with the Department of Defense is specific to the evaluation of the use of plasma in the field. As described above, the majority of potentially survivable injuries are due to hemorrhage. If administering plasma earlier in the field decreases hemorrhage from acute coagulopathy of trauma, injured members of the armed forces may have more time to reach a facility to be better stabilized and resuscitated. Although some institutions have adopted the principle of early plasma administration in the management of severe trauma and the acute coagulopathy of trauma, there are no prospective studies measuring the benefit and risks of administering plasma early.

Although this is a greater than minimal risk study, subjects are likely to receive direct benefit from this clinical trial from closer evaluation and testing of coagulation status. Based on the previous retrospective studies and preclinical studies described in the Section II.A. (Background) and Section III.A. (Preliminary studies) as well as our current understanding of administering plasma earlier and more frequently in the resuscitation of patients in severe hemorrhagic shock, patients receiving early plasma are likely to directly benefit from this study.

This study will be carried out in accordance with 21 CFR §50.24 Exception from Informed Consent for Emergency Research.

N. Description of Risks, Benefits and Justification

 Risk of blood transfusion: These risks apply to any patient that receives blood products regardless of group assignment. Both the standard and experimental groups are likely to receive blood products during the resuscitation period, but

the study group will receive at a minimum 2 units of AB plasma. In this study, all plasma used as an initial resuscitation fluid will be AB and hence universally infusible without the requirement for patient blood typing. This is the usual type of fresh frozen plasma used in acute trauma setting prior to obtaining type and cross

Table 3: Risk of Disease from Blood Product Transfusion				
Transmitted Blood Product Disease	US Transmission Risk/Unit Transfused			
Hepatitis A Virus (HAV)	1:8,300,000			
Hepatitis B Virus (HBV)	1:282,000			
Hepatitis C Virus (HCV)	1:1,149,000			
Human Immunodeficiency Virus (HIV-1, -2)	1:1,467,000			
Malaria	1:4,000,000			
Human T-cell lymphotrophicvirus (HTLV-I, -II)	1:2,990,000			

match (see appendix 9 for adult transfusion guidelines). Risks of blood

transfusion include febrile non-hemolytic transfusion reaction (1.1% to 2.5%), hemolytic transfusion reactions (1:1,250,000), transmission of blood borne pathogens (See Table 2), transfusion-related lung injury (TRALI) (8.1 per 100,000), transfusion associated circulatory overload (TACO) (2-3 per 100).¹¹² A blood transfusion may also result in a reaction that includes fever, chills, or hives. Although uncommon, the patient may experience this type of reaction as the result of receiving the incorrect type of blood. By using AB type of plasma, this risk is minimized. This risk is minimized in the blood bank by a questionnaire to exclude donors who are at risk of having a blood borne pathogen as regulated by the FDA under 21CFR 640 subpart G. The donated blood is also tested in the laboratory for infectious diseases.

A blood transfusion may increase the likelihood of developing an infection while the patient is in the hospital, may exaggerate how the patient's body responds to injury, and may increase the patient's risk of internal organ failure after his/her injury.

Excessive transfusions place patients at higher risk of hypervolemia, and pulmonary edema, but this risk also exists for patients who receive excessive intravenous fluids. The risk of 2 units of AB-FP24 as initial resuscitation leading to cardiac failure, hypervolemia and pulmonary edema is low as it is a smaller volume (500ml) than the standard 2 liters of crystalloid intravenous fluid. These risks exist with transfusions of any blood products

- Risk of Inadvertent Release of Protected Health Information (PHI): This risk is minimized by using a unique patient identifier and role based security for the database. All hard copies will be kept locked in the research office or be destroyed.
- **3.** Venipuncture risk: In most cases blood will be drawn from an intravenous line (I.V.) already placed as part of the patient's standard medical care. In the event the patient does not have an I.V., blood will be drawn using a method known as venipuncture. This procedure consists of placing a small needle in a vein in the patient's arm to withdraw blood. Risks associated with drawing blood from the patient's arm include pain, bruising, lightheadedness, and rarely infection.
- 4. Potential Scientific Problems: Potential scientific problems include the possibility our hypothesis will not increase survival, improve MOF, and decrease the need to blood products. We feel this possibility is low given the background and preliminary studies that have been done, however, we will evaluate the outcomes at each interim analysis to detect early if our hypothesis is incorrect. Another potential scientific problem may be the enrollment of patients who are nonvisibly pregnant, or younger than 18 years of age, during the hospital stay. Age is often estimated at the time paramedics arrive to the scene and some patients may appear to be 18 years of age or older but may truly be younger. We plan to minimize the potential to enroll pregnant or potentially pregnant women and patients less than 18 years, by recommending they opt out with the bracelet and necklace ID. Other potential scientific problems include the risk of unforeseen events such as thrombotic events of myocardial infarction, stroke, and venous thromboembolism. We will monitor for these events in the study

patients and determine if administration of plasma leads to increased thrombotic events. Upon discovery of these events, it will be reported to the Data Safety Monitoring Board. The risk of this is low since these patients are hypocoagulable and at risk for bleeding. Finally, the study is not blinded to clinicians. Thus, there may be a treatment bias to withhold blood transfusions for borderline values in the study arm for a longer time or to transfuse those in the standard arm quicker. However, the initial resuscitation occurs in the ambulance, where the patient is randomized. The majority of the resuscitation occurs in the Operating Room, often driven by the anesthesia team or the Surgical Intensive Care Unit, driven by the ICU team, who may have no knowledge which study arm the patient is enrolled in or if the patient is enrolled at all.

- 5. Risk to Investigator or Institution. There is no known direct risk to the Investigator or Institution. However, the transmission of viruses may occur through contact with contaminated needles and blood or blood products. Accordingly, all study personnel involved in the collection of blood and/or handling of specimens will employ appropriate blood and body fluid precautions in the both the clinical and laboratory settings.
